DATA SAFETY MONITORING PLAN

NIH Grant number: R21 DA041114-01A1

Targeted Pharmacological and Behavioral Treatments for
Smoking in Schizophrenia

Principal Investigator: [name]., Brown University

Medical Monitor: [name]., Ph.D., Brown University

Version Date: May 19, 2017

Summary of the Protocol

Brief Description of Protocol

The prevalence of cigarette smoking among people with schizophrenia in the United States is two- to three-times that of the general population. Smokers with schizophrenia (SS) have very low rates of smoking cessation, resulting in a disproportionate burden of tobacco-related morbidity and mortality. The overall objective of this project is to develop a novel, theory-driven intervention for smoking cessation for SS. Varenicline (VAR) reduces relapse among SS who attain abstinence, but is less effective at inducing abstinence. Contingency management (CM) interventions are highly effective at inducing abstinence in SS, but relapse rates are high once the incentives are discontinued. The combination of VAR + CM may be optimal for both inducing abstinence and reducing relapse in SS, especially if VAR reduces target mechanisms that are posited to underlie early relapse in SS: smoking urges and negative affect during abstinence (primary targets), smoking reinforcement (reward and satisfaction) during a smoking lapse (secondary targets) and cognitive dysfunction during abstinence (exploratory target). In the R21 phase of this research, we will use a laboratory model to compare the effects of VAR and placebo (PLA) on time to relapse and on these primary, secondary and exploratory target mechanisms.

Aims of the R21 Phase

Aim 1: To examine the effects of VAR versus placebo (PLA) on smoking urges and negative affect during abstinence, reinforcing effects of a smoking lapse, cognitive function and time to relapse in SS.

Aim 2: To examine the extent to which the effects of VAR on time to relapse are mediated through its effects on the target mechanisms.

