A total of 48 randomized participants are planned for the R21 phase. This sample size is based on Aim 1, which is to determine effects of VAR versus PLA on smoking urges and negative affect during abstinence, reinforcing effects of a smoking lapse, cognitive function and time to relapse in SS. A repeated-measures design with 48 total participants provides 80% power to detect main and interaction effects on the primary targets (smoking urges and negative affect during abstinence) and secondary targets (reinforcing effects of a smoking lapse) of at least $d = .40$ in size, assuming a moderate within-subject autocorrelation. While this effect size is somewhat smaller than those detected by West et al. (2008) for effects of abstinence on urges and negative affect during abstinence and smoking satisfaction and reward from relapse (d 's = .32-.44), abstinence was not controlled or biochemically verified after target quit date in that study, and, as the authors noted, it is possible that the effects that they observed were due only to those who were completely abstinent. With our rigorous control of abstinence, which includes twice-daily CO testing and a stringent abstinence criterion, we believe that we will detect smaller effects. We are not determining sample size based on Aim 2 (which is to examine the extent to which the effects of VAR on time to relapse are mediated through its effects on the target mechanisms), but we should be able to

detect medium-sized group effects on latency to second lapse, and estimate the size of mediation relationships that would be detectable as significant. We anticipate 20% attrition between enrollment and randomization. Therefore, we anticipate needing to enroll up to 60 participants (30 per group) to include 48 in the intent-to-treat sample.

R33 phase:

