Mediation of the relationship between group and lapse latency will be examined using an SPSS macro (Preacher & Hayes, 2004). Hypothesized mediators will include baseline Calgary scale, cognitive performance and Contemplation Ladder scores, Session 8 QSU and MNWS scores, Session 8 CPT and CEQ Reward and Satisfaction scores, and Session 8 cognitive performance scores. Simple mediator models will be used to investigate the direct effect of medication on relapse latency (c path) with no mediator in the equation, as well as the medication \rightarrow mediator path (a), the mediator \rightarrow latency path (b), and the effect of medication on latency with the mediator in the equation (c' path). The indirect effect of medication on latency via each mediator ($c - c'$) is equal to the product of the coefficients of the "a" and "b" paths (i.e., "ab"). If ab is not normally distributed, 10,000 bootstrap resamples will be used to obtain lower and upper 95% confidence intervals (CI) for each indirect effect (Preacher & Hayes, 2008). All variables will be standardized first so that path coefficients can be directly compared across variables with different metrics. In addition, step-wise regression will be used to examine whether screening BPRS scores (entered in Step 1) and Session 8 BPRS scores (Step 2) predict latency to relapse. The SPSS mainframe statistical package (SPSS, Inc., Chicago, IL) will be used for GEE, mediation and regression analyses. All other analyses will be conducted using SPSS Statistics Version 20 for Windows (IBM, Armonk, NY). Differences will be considered significant when $p \leq .05$.

R33 phase

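### The R21 mediation plan bootstraps the indirect effect only if ab is judged non-normal, with no criterion and no named alternative; the condition is either redundant or harmful and should be deleted

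*Combined protocol and SAP*

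**What the plan says.** Aim 2 of the R21 phase (Summary of the Protocol, Aims of the R21 Phase) is the mediation question: "To examine the extent to which the effects of VAR on time to relapse are mediated through its effects" on the target mechanisms. The Data Analysis Plan, R21 phase, gives the method: "Mediation of the relationship between group and lapse latency will be examined using an SPSS macro". Simple one-mediator models are fitted to a long list of candidate mediators, and the indirect effect is the product ab of the medication-to-mediator and mediator-to-latency coefficients.

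The only rule for inference on ab is conditional: "If ab is not normally distributed, 10,000 bootstrap resamples will be used", to give a 95% interval for each indirect effect. The plan gives no criterion for deciding whether ab is normal and names no procedure for the case where it is. The general significance rule in the same section is "Differences will be considered significant when $p \leq .05".

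The sample is set out under Power Calculation and Sample Size, R21 phase: "A total of 48 randomized participants are planned for the R21 phase". That section says the number was not chosen with Aim 2 in mind, and it states no power for mediation.

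**The concern.** One trial yields one ab per mediator. Its sampling distribution cannot be observed; it can only be approximated by resampling or assumed. A rule that turns on whether ab is normal therefore cannot be applied as written until someone supplies a criterion, and the choice would be made with the data in hand.

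If ab is judged normal, the natural alternative is a symmetric normal-theory interval (ab ± 1.96 standard errors, the Sobel approach). For a product of two estimates in a small sample this interval has low power and falls short of 95% coverage when the effect is real. At stake are whether a true indirect effect is seen under Aim 2, and whether mediators are judged by one standard. The second matters because the plan standardises all variables so that paths can be compared across mediators.

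**Working it through.** **Inputs from the documents**
- Randomised sample: 48. The plan's own figure reproduces: "We anticipate 20% attrition between enrollment and randomization", so 48 / (1 − 0.20) = 60, matching "we anticipate needing to enroll up to 60 participants (30 per group) to include 48 in the intent-to-treat sample". Equal groups give 24 per arm.
- Significance level 0.05, taken as two-sided because the interval has a lower and an upper limit.
- Latency is capped at 192 h (Data Analysis Plan, R21 phase).
- The Session 8 smoking procedure is for continuously abstinent participants (Brief Description of Protocol), so models with Session 8 mediators may have fewer than 48.

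**Assumptions**
- The documents give no a-path or b-path size, so a range is used. a is the group difference in the mediator in SD units; b is the mediator-to-latency slope.

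**Why the normal-theory test is weak here**

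The statistic is z = ab / √(a²·se_b² + b²·se_a²). Dividing through by ab gives z = 1 / √(1/z_a² + 1/z_b²), where z_a = a/se_a and z_b = b/se_b. It is always smaller than the weaker of the two path statistics. If both paths sit exactly at 1.96, z = 1.96/√2 = 1.39.

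Worked case, a = 0.5, b = 0.39, 24 per arm:
- se_a = √(1/24 + 1/24) = 0.289, so z_a = 1.73.
- Residual SD of the outcome = √(1 − 0.39²) = 0.921; se_b ≈ 0.921/√46 = 0.136, so z_b ≈ 2.87.
- z ≈ 1 / √(1/1.73² + 1/2.87²) = 1.48, below both.

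**Simulated power at n = 48**

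Model: mediator = a·group + noise; outcome = b·mediator + noise; no direct effect; 4,000 trials with 1,000 resamples each (1,500 trials for the last row).

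| a | b | Normal-theory | Percentile bootstrap | Gap (points) |
|---|---|---|---|---|
| 0.4 | 0.30 | 4.7% | 14.3% | 9.6 |
| 0.4 | 0.39 | 9.7% | 21.7% | 12.0 |
| 0.5 | 0.39 | 16.6% | 31.2% | 14.6 |
| 0.8 | 0.39 | 41.3% | 61.0% | 19.7 |
| 0.8 | 0.59 | 71.0% | 78.7% | 7.7 |
| 1.2 | 0.59 | 96.7% | 98.2% | 1.5 |

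A second model, with a direct effect of 0.2 and unit residual SDs, gave across repeat runs:
- a = 0.6, b = 0.4: 20–21% v 38–39%
- a = 0.8, b = 0.4: 37–38% v 58–59%
- a = 0.8, b = 0.5: 52–54% v 69–72%

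Repeat runs of the two smaller scenarios gave 4–5% v 12–14% (a = 0.4, b = 0.3) and 14–17% v 28–33% (a = 0.5, b = 0.39).

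**Variations at a = 0.5, b = 0.39**
- Outcome capped to mimic the latency ceiling: 14.0% v 31.0%.
- n = 36 (an assumed loss of a quarter): 8.6% v 21.3%.

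**Coverage, error and agreement**
- Coverage for non-null effects: normal-theory about 91–93%, percentile bootstrap about 94%.
- False positives with a = 0, b = 0.39: normal-theory 1.0%, percentile 3.7%, bias-corrected bootstrap 6.9%.
- The two methods reach opposite conclusions in 8–22% of non-null trials.

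**Can the condition be checked?**

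The skewness of ab at n = 48 was 0.45 to 0.87 over four scenarios. A normality test on 10,000 bootstrap draws rejected in all 200 trials of each scenario; with 1,000 draws it rejected in 96–99% of trials. Checked this way, the condition nearly always leads to the bootstrap and adds nothing. Checked otherwise (on the raw variables, by eye or by a weak test), it can admit the inferior interval.

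**The case against.** The tempting stronger reading is that the plan defaults to a Sobel test and so gives up much of its mediation power. The documents do not say that. No normal-theory test is named and nothing is called a default; the one method named for ab is the bootstrap. An analyst who checks normality on bootstrap draws would end up bootstrapping, and the power loss would not arise. This objection stands: the loss is a risk that the wording allows, not one that the plan commits to.

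A reader might also infer that different mediators will be judged by different methods. The sentence can equally be read as bootstrapping every indirect effect once non-normality is accepted. Mixed treatment is possible but not stated.

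The size of the gap depends on path sizes that the documents do not supply. The power section works with a standardised effect of .40, and at a = 0.4 both methods have low power. The normal-theory branch is conservative, so it would not produce false claims of mediation. Finally, Aim 2 did not set the sample size, and the go/no-go rule turns on reductions in the targets, not on mediation.

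All of this limits how much the point matters. None of it supplies the missing criterion or the missing alternative, or gives a reason to keep the condition.

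**Conclusion.** The point holds in limited form. The sole inference rule for a stated aim depends on a judgement that the plan does not define, and it leaves the other branch unspecified. That permits a normal-theory interval for some or all mediators. At 24 per arm or fewer, the condition either changes nothing or lets in a worse interval.

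If the normal-theory interval were used, power would be roughly one third to two thirds of the percentile bootstrap's when at least one path is small to medium (4.7/14.3 = 0.33; 41.3/61.0 = 0.68). With both paths large, the loss is about 8 points, falling to 1–2 points at very large paths. These figures rest on assumed path sizes, linear models, 1:1 allocation and a two-sided 0.05 level.

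It should not be inferred that the change makes Aim 2 adequately powered. At a = 0.5, b = 0.39 the percentile bootstrap still has only about 31% power, and the plan claims none. Severity is minor to moderate.

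**What to change.** In the mediation paragraph of the Data Analysis Plan, R21 phase, delete the normality condition. State that every indirect effect is estimated with, and judged by, a 10,000-resample percentile bootstrap 95% confidence interval, whatever the apparent distribution of ab.

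Name the interval type, because the plan does not. The percentile form kept false positives at about 4% in the simulations, while the bias-corrected form reached about 7%.

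The cost is one sentence and minor computation; the plan already provides for 10,000 resamples. Sample size, data collection and the go/no-go rule are unaffected.

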In Session 1 (pre-medication baseline), we will collect baseline measures of smoking urge, withdrawal symptoms, mood, cognitive performance, a behavioral economics-based measure of cigarette demand and effects of smoking a cigarette on cigarette reward, satisfaction and mood. Next, participants will be randomized to VAR (1 mg twice daily for 3 weeks) or PLA, using urn randomization to stratify on gender and dependence. Participants will complete a week of medication use using the standard dose run-up (0.5 mg once daily on days 1-3, 0.5 mg twice daily on days 4-7, then 1 mg twice daily until the end of the medication period). In Session 2, which occurs after one week on medication, participants will complete the same laboratory assessments as in Session 1. Next, participants will undergo a 3-day abstinence period. They will come to the laboratory twice per day and will receive escalating cash incentives for breath carbon monoxide (CO)-verified abstinence. At each visit, cigarette craving and withdrawal symptoms will be measured. At Session 8 (Thursday morning), participants who have been continuously abstinent will complete the same procedure as in Sessions 1. For ethical reasons, participants who complete the study through Thursday and who wish to remain abstinent may opt out of smoking during this session and will still receive full compensation for participation, as long as they attend this lab session and complete the other session measures.

Participants will be asked to return to the laboratory on Friday morning. Breath CO will be measured and time of first lapse (single cigarette) and relapse (return to regular smoking) will be collected among those who have lapsed and relapsed. Those still abstinent ($CO \leq 4$ ppm) since Session 8 will receive a small cash incentive. Next, participants will be shown how to use breath CO monitors with smart phones to record

and text us videos of themselves providing CO samples twice per day for the following week to determine time to lapse and relapse. Participants will receive \$5 for each submitted sample (not contingent on CO level), paid when the smart phone and CO monitor are returned at the end of the week.

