All data will be collected for research purposes only. All forms will be marked with only subject ID, session number and date. All records will be stored in locked files (physical or on computer) in locked rooms accessible only to research staff. Data gathered from people who attend the screening but do not meet inclusion criteria or decide not to participate will be stripped of personal identifiers or links and only the reason for study exclusion will be kept.

Personal information (participant name, address, telephone number, email address, locator contact information) must be collected so that the research assistant can contact people to schedule assessments, call with session reminders and arrange transportation to sessions. These data will be stored in a locked file that does not contain ID code numbers. All other data will be stored in files locked in a separate location with only code numbers identifying subjects and no personal identifiers. A cross-index of code numbers and participant names will be kept in a separate, password-protected computer file that is available only to research staff, PI, and mandated agencies during audits (e.g., study sponsor and Brown University IRB).

Saliva specimens for cotinine analysis will be marked with a study ID number, stored in the locked laboratory suite, and sent to a commercial laboratory for analysis. We will track samples sent and analysis results received using a form stored on a password-protected computer.

Data Analysis Plan

R21 phase

Variables will be examined for distributional assumptions associated with analyses to be used and transformed if necessary. Groups will be compared on demographic and other individual difference measures using t-tests for continuous measures and chi-square tests for categorical measures. Analyses of the effects of Group (VAR, PLA) and Time (Sessions 2-8) on QSU and MNWS-negative affect scores will be conducted using generalized estimating equation (GEE) models (Zeger et al., 1988), which allow for varying numbers of observations per participant (to minimize bias due to attrition) while controlling for autocorrelation (AR1 structure). GEE will also be used to analyze the effects of Group and Time (Screening, Sessions 2 and 8) on BPRS and other psychiatric symptom scores. Mixed 2 x 2 Analysis of Variance tests (ANOVAs) will be used to examine effects of Group and Abstinence (Sessions 1 and 8) on CEQ scale scores,

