cognitive measure scores (with baseline scores covaried), CPT demand indices and within-session changes (post- minus pre-smoking) in CO level and positive and negative mood scale scores. Significant interactions will be followed by simple effects tests. Those who opt not to smoke in Session 8 will not be included in the Group x Abstinence analyses of CEQ, or pre-to-post smoking changes in CO or mood, but will be included in all other analyses (only one SS opted not to smoke in Session 8 in our previous study, Tidey et al., 2014). Latency to relapse will be defined as hours between the start of Session 8 and time of relapse, collected in person at Friday's session and by videoed CO sample in the follow-up week. We will follow up for one week after Friday's session, which is 8 days after Session 8. Thus, the maximum latency until second lapse will be 192 h, at which point data will be censored. Lapse latencies will be compared in VAR vs. PLA using a t-test. We will examine whether gender and FTND score (≤ 5 vs. ≥ 6) moderate the effects of VAR by adding these factors (separately) to each model.

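### The R21 regression of relapse latency on BPRS omits treatment arm, so a drug effect on both Session 8 BPRS and latency would partly show up in the Step 2 coefficient

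*Combined protocol and SAP*

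**What the plan says.** The Data Analysis Plan for the R21 phase ends its mediation paragraph with an additional analysis of latency to relapse: "step-wise regression will be used to examine whether screening BPRS scores (entered in Step 1) and Session 8 BPRS scores (Step 2) predict latency". Only the two BPRS scores are named as predictors.

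The protocol summary places randomization after Session 1: "participants will be randomized to VAR (1 mg twice daily for 3 weeks) or PLA, using urn randomization to stratify on gender and dependence". Session 8 comes after a week of medication and a three-day abstinence period, so Session 8 BPRS is a post-randomization measurement. Screening BPRS is not.

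The same plan treats arm effects on both variables as open questions. On symptoms: "GEE will also be used to analyze the effects of Group and Time (Screening, Sessions 2 and 8) on BPRS and other psychiatric symptom scores". On latency: "Lapse latencies will be compared in VAR vs. PLA using a t-test". The Power Calculation section adds that the study should be able to "detect medium-sized group effects on latency to second lapse".

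Nothing else in the documents puts arm into the BPRS regression:
- The mediation models carry medication, but BPRS is not among their mediators. The list opens "Hypothesized mediators will include baseline Calgary scale, cognitive performance and Contemplation Ladder scores, Session 8 QSU and MNWS scores" and goes on to the Session 8 CPT, CEQ and cognitive scores.
- The sentence on extra factors, which applies to every model, covers only moderators: "We will examine whether gender and FTND score (≤ 5 vs. ≥ 6) moderate the effects of VAR by adding these factors (separately) to each".

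**The concern.** Step 2 uses a predictor that treatment may have altered to explain an outcome that treatment is expected to alter. If both effects exist, the two arms differ in mean BPRS and in mean latency. Pooling them then creates an association even when symptoms and latency are unrelated within each arm.

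The neighbouring mediation models estimate the path from each mediator to latency with medication in the equation. BPRS is the one Session 8 measure related to latency without it, and no reason is given. In a trial about why smokers with schizophrenia relapse, a significant Step 2 result would readily be read as symptoms bearing on relapse when it may partly stand in for arm.

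**Working it through.** The plan gives no effect size, power or R-squared for this regression, so there is no stated figure to reproduce. The check asks how often Step 2 would be significant if BPRS had no relation to latency within either arm.

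**Inputs from the documents**
- Predictors and their order: Data Analysis Plan, R21 phase.
- Sample size: "A total of 48 randomized participants are planned for the R21 phase" (Power Calculation and Sample Size). Equal arms give 48 / 2 = 24 per arm.
- Threshold: p ≤ .05 (Data Analysis Plan, R21 phase). Sidedness is not stated; two-sided is assumed.
- Effect on latency: described only as medium, taken here as about .5 SD. The plan uses relapse, lapse and second lapse for this latency; they are treated as one outcome.

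**Assumptions, not in the documents**
- ρ, the correlation of screening with Session 8 BPRS: .5 to .7.
- a, the reduction in Session 8 BPRS on drug: 0 to .8 SD.
- c, the lengthening of latency on drug: 0 to .8 SD.
- Normal data; censoring at 192 h not modelled.

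**Step 1: expected false slope.** With equal arms the arm indicator has variance 1/4. After screening BPRS is partialled out, Session 8 BPRS has variance (1 − ρ²) + a²/4 and covariance −ac/4 with latency. In within-arm SD units the Step 2 slope is therefore

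b = −(ac/4) / [(1 − ρ²) + a²/4].

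For a = c = .5 and ρ = .5: b = −.0625 / (.75 + .0625) = −.077.
For a = c = .8 and ρ = .7: b = −.16 / (.51 + .16) = −.239.

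**Step 2: simulation.** 24 per arm, ordinary least squares, 20,000 replicates per row. The last two columns are the rejection rates for Session 8 BPRS.

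| BPRS effect (a) | Latency effect (c) | ρ | b, formula | b, simulated | As written | With Group |
|---|---|---|---|---|---|---|
| .2 | .5 | .5 | −.033 | −.034 | 5.4% | 5.1% |
| .2 | .5 | .7 | −.048 | −.047 | 5.8% | 5.2% |
| .5 | .5 | .5 | −.077 | −.077 | 7.3% | 5.1% |
| .5 | .5 | .7 | −.109 | −.112 | 8.4% | 5.1% |
| .5 | .8 | .5 | −.123 | −.125 | 10.4% | 4.9% |
| .5 | .8 | .7 | −.175 | −.179 | 13.0% | 4.9% |
| .8 | .8 | .5 | −.176 | −.178 | 18.0% | 4.9% |
| .8 | .8 | .7 | −.239 | −.246 | 23.8% | 4.8% |

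At ρ = .6, further runs gave 5-6% at .2/.5 SD (BPRS/latency), about 7% at .5/.5, 11-12% at .5/.8 and 19-21% at .8/.8.

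**Step 3: where the bias enters.** If the drug affects only one of the two variables, the rate stays at 4.8-5.0%. Screening BPRS in Step 1 stays at 4.7-5.2% throughout. Once Session 8 BPRS is added, the screening coefficient is distorted too, with rejection up to 12.8%. With Group in the model, the Session 8 slope averages zero to within .002.

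**Step 4: fewer participants at Session 8.** At ρ = .6 with 16 or 12 per arm (assumed), the .5/.5 rate is 6.4% or 6.0%. The .8/.8 rate falls from 21% to 15% or 12%.

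**Step 5: direction.** If VAR lowers BPRS and lengthens latency, b is negative, which mimics or exaggerates a link in which worse symptoms shorten latency. Masking such a link needs a positive bias: VAR would have to raise both BPRS and latency.

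**The case against.** The strongest reply is that the plan asks only whether BPRS predicts latency. It makes no causal or within-arm claim, and the causal models are specified separately without BPRS. That stands: the pooled regression is valid as crude forecasting. The difficulty begins only when the result is read as a relation between symptoms and relapse, and its place beside the mediation models invites that reading.

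The documents also give little reason to expect a sizeable drug effect on BPRS. The section on potential risks cites a large trial with no excess of neuropsychiatric events on varenicline and rates the risk of symptom change from altered smoking as low. This stands too, and makes the upper rows of the table more relevant than the lower ones.

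Session 8 is described for continuously abstinent participants and latency is counted from it, so fewer than 24 per arm may contribute. The documents give no number. A smaller sample lowers the false-positive rate but leaves the expected slope unchanged.

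Finally, readers can check the precondition, since Group effects on BPRS and on latency are both tested. This helps only partly. With 24 per arm, a single two-group comparison such as that of latency has about 41% power at .5 SD and 79% at .8 SD (normal approximation), so a non-significant arm effect would not exclude the bias.

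A reader might infer that any drug effect at all would appear as symptoms predicting relapse, that the screening score is equally compromised, or that the main results are at risk. The documents and figures do not support this. Both drug effects are needed, and small ones leave the rate close to 5%. Screening BPRS precedes randomization. BPRS is a secondary outcome that plays no part in the R21 aims or the go/no-go rule. Nor would masking follow from VAR lowering BPRS while lengthening latency; Step 5 of the working shows the opposite.

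**Conclusion.** The point holds in a limited form. The regression as written has no arm term, no other section supplies one, and its Step 2 coefficient mixes any symptom-relapse relation with arm differences if VAR affects both variables. At the medium latency effect the plan mentions, the inflation is slight; it becomes clear only when the effect on BPRS is at least medium and the effect on latency is large. All sizes rest on the assumed effects, the assumed BPRS correlation, 24 per arm and no censoring. This is an inexpensive improvement to a secondary analysis, not a flaw in the trial's main comparisons or sample size.

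**What to change.** In the Data Analysis Plan for the R21 phase, enter Group together with screening BPRS in Step 1 and Session 8 BPRS in Step 2. State that the arm-adjusted Session 8 coefficient is the one to interpret, and that it is an observational association: adjustment removes confounding by arm, but symptoms are not randomized within arms, and a single slope assumes the relation is the same in both. A Group by Session 8 BPRS term could be examined as a check on that. If crude prediction is what is wanted, say so and report the unadjusted model beside the adjusted one. The cost is a phrase in the plan and one degree of freedom, with no new data.
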